The cause of the low DHA is not clear, but the improvement of DHA by LA supplementation suggests that it might not be of primary importance (Farrell et al 1985, Strandvik et al 2001) and maybe associated with a high phospholipid turn-over (Bhura-Bandali et al. 2000, Strandvik 2010, Rogiers et al 1984). However, long-term studies in CF mice and a recent paper suggest that the ratio between AA/DHA in blood cell tissues is related to the liver disease in CF, suggesting that the concentrations of polyunsaturated fatty acids (PUFA) might contribute to the unexplained liver affection in many of the patients (Lindblad et al. 1999; Beharry et al. 2007; van Biervliet et al 2010; Jørgensen et al. 2012, Drzymala-Cryz et al, 2017). Because one study of transgenic CF mice showed low DHA associated with morphological changes in ileum and pancreas (Freedman et al 1999), although later not confirmed in a long-time study (Beharry et al 2007), many clinical trials with supplementation of omega-3 LCPUFA started, but mainly failed to show clinical improvement despite marked increase of omega-3 fatty acids in plasma (van Biervliet et al. 2008, Oliver et al. 2011, Alicandro et al. 2013). One study with regular intravenous supplementation of omega-3 for 3 months even showed negative impact on the patients (Durieu et al. 2007). As mentioned above one study showed

marked clinical improvement by a combination of omega-3 and omega-6 supplementation (Oliveira et al. 2010).

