It is well known that low LA concentrations are associated with high AA concentration, while supplementation with LA decreases the AA concentration (Liou et al. 2007, Friesen et al 2010, Bjermo H et al 2012, Wheelock & Strandvik 2020). In healthy individuals no increase of inflammatory markers have been reported with omega-6 supplementation (Bjermo et al 2012, Johnson GH & Fritsche K 2012). This is of importance since the release of AA is the rate-limiting step for eicosanoid production, which is increased in CF (Strandvik a Seybert 1996, Chase & Dupont 1978, Jabr et al 2013). In one study of 10 months supplementation of LA in CF patients prostaglandin F2 α production decreased (Chase & Dupont 1978). Ivacaftror did not influence LA concentration but decreased AA concentration in plasma and decreased PGE-M in urine in the GOAL study for patients with G551D mutations (O'Connor & Siegmiller 2016). These studies show that both LA and CFTR modulators might influence lipid metabolism and decrease inflammatory mediators. Despite this fact, the lack of good randomized clinical studies have made many centers hesitate to supply LA because it's a substrate for AA and thereby also for the pro-inflammatory lipid mediators. High AA concentrations have been found in bronchial secretions in CF (Gilljam et al 1986) and was confirmed in a recent study of sputum from CF patients (Yang J, et al 2012)

In a recent double-blind randomized trial high AA concentration in plasma was associated with low NO in the airways of CF patients (Keen et al. 2010). Low NO can contribute to pseudomonas colonization, which is considered a threat for

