The fatty acids will be given daily for 12 months, in vials containing an emulsion of totally 20 ml (provided by AKK Company, Karlshamn, Sweden and Copenhagen Denmark, packed by WinterMedic, Odense, Denmark), which can be mixed with milk, juice, sour cream, porridge or any similar feeding at breakfast time. Some extra enzymes may be added.

The treatment will last 12 months, starting and ending at time of the yearly check up of the patients. Half the number of patients will be randomly allocated to receive either treatment A or B. An independent researcher (not involved in the study) will generate the allocation sequence at each center. This will reduce small differences in local treatment policy. The vials with supplementation will only be coded (black or white capsula) so neither patient nor caregivers or staff in charge will be informed by the type of supplementation.

Primary Outcome

- BMI Z-score, weight-Z-score

Secondary outcomes

- Height Z-score
- FEV1 (% of predicted) and oxygen saturation
- Exacerbations and infectious parameters compared to year before.
- Plasma phospholipid fatty acid profile.
- Plasma concentration of IGF-I

Explanatory outcomes

- Bone mineral density
- Lean body mass and fat mass.
- Liver function tests
- Lipid mediators (like eicosanoids and docosanoids)
- Cytokines
- 8-iso-prostane
- Sweat sodium and chloride concentrations
- Renal sodium excretion
- Resting energy expenditure
- Intestinal function (fecal calprotectin and fat absorption coefficient)
- Oral glucose tolerance with insulin determination.

METHODS

Patients will be screened for enrollment and will be allocated to one of the treatment at baseline visit. Follow-up visits will be scheduled at 6 and 12 months after treatment allocation. Some measures, like fat absorption coefficient and calprotectin and resting energy expenditure, exhaled NO and ergometer test will not be performed in all patients due to limited capacity at some centres. The study procedures are summarized in table 1.

Table 1. Outline of study procedures

	Baseline visit: Screening and allocation	+6 months	+12 months
Anthropometry	X	X	X
DXA	X		X
FFQ	X	X	X
24-h dietary recall	X	X	X
Pulmonary function	X		X
Blood sample	X	X	X
F-Calprotectin	X		X
Urine sample	X		X
Ergometer test with oxygen saturation	X		X
Oral glucose tolerance	X		X
Indirect calorimetry	X		X
Sweat test	X		X
Compliance to treatment	X	X	X
CF Questionnaire	X	X	X

1. *Anthropometry.*

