Height and weight are controlled with the same equipment for each patient at respective centre and at each scheduled visit (baseline, 6 and 12 months after allocation). Z-scores of weight, height and BMI will be computed using WHO as growth standard. DXA is performed at start and after 12 months period for determination of bone mineral content and density, lean body mass and fat mass.

1. *Food registration.*

- Food frequency questionnaire (FFQ) will be performed at start and each scheduled visit, mainly used for calculation of energy intake and intake of fat and fatty acids (validated questionnaire Eriksson S et al. 2010). Since the products are different in different countries the FFQ form can only suggest **type** of products to be evaluated, complemented by the local dietician. The reason to include these registrations is to individually make a comparison with intake at start and end of study possible, checking that not major changes have occurred in diet, which can influence the results.
- 24-hour recall will be performed at start, 6 months and 12 months after allocation as a complement to FFQ for portion size, type of products etc.

3. *Pulmonary function.*

- Routine pulmonary function (FEV1) at each clinical visit
- Full spirometry at start and end of treatment
- Exhaled NO (if available)
- Ergometer test at start and end
- Oxygen saturation (ear-tip).

4. *Biochemistry.*

- Routine blood biochemistry (fasting) at start and end of treatment period, including Hb, platelets, white blood cell count and differential count, ASAT, ALAT, alkaline phosphatase, GGT, PK, total and conjugated bilirubin, bile acids, cholesterol, lipoproteins, triglycerides, urea, creatinine, glomerulus filtration rate. Ig-G, CRP, sedimentation rate.

- 1 ml serum/plasma for later analyses (to freezer divided in 4 tubes for later analyses of lipid mediators at KI).
- 0,5 ml for IGF-I analysis (to freezer for later analysis in Sweden)
- 0.5 ml plasma for cytokines (to freezer for sending to Stockholm for analyses (OLINK, Uppsala, Sweden).
- 0.5 ml plasma for analyses of phospholipid fatty acids (to freezer for later analysis in Poznan or Stockholm).
- Urine sample for routine tests, incl sodium and creatinine concentrations.

5. *Intestinal function*

- F-Calprotectin at start and after 12 months (in freezer for later analyses at one center)
- Fat absorption at start and 12 months. Three day dietary recording and feces

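### Table 1 and Methods 3 and 4 do not say clearly what is measured at 6 months: blood is drawn with no stated use, no routine liver, blood-count or CRP result is scheduled on the Methods text, and FEV1 has no 6-month entry

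*Protocol*

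**What the plan says.** Two parts of the protocol define the 6-month visit.

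- **Blood, Table 1 (METHODS).** The row reads "Blood sample X X X", that is, baseline, +6 and +12 months. It does not say which tests the sample serves.
- **Blood, Methods section 4 (Biochemistry).** The routine panel is timed as "Routine blood biochemistry (fasting) at start and end of treatment period", "including Hb, platelets, white blood cell count and differential count, ASAT, ALAT, alkaline phosphatase" and so on through bilirubin, lipids and renal tests to "Ig-G, CRP, sedimentation rate". The same section lists four stored aliquots: lipid mediators, IGF-I, cytokines and phospholipid fatty acids. None has a visit attached, and all go to the freezer, for example "0.5 ml plasma for cytokines (to freezer for sending to Stockholm for analyses".
- **Lung function.** Methods section 3 asks for "Routine pulmonary function (FEV1) at each clinical visit" and, as a separate item, full spirometry at the start and end of treatment. Table 1 has one pulmonary function row, marked at baseline and +12 months only.

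FEV1, IGF-I and the fatty acid profile are secondary outcomes; liver function tests are in the explanatory list. The mixed model in section 9 (Statistics), repeated in the SAP, is specified for the primary outcome only. Secondary and explanatory outcomes get a paired t-test or a signed-rank test.

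**The concern.** A centre cannot tell from the protocol whether the 6-month blood should go for routine tests, to the freezer, or both, or whether the 6-month FEV1 is study data. Centres may resolve this differently, and their files are then pooled for one analysis.

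Two things are at stake. The first is information during treatment: if Methods section 4 is followed, the first routine liver, blood-count or CRP result after baseline comes when 12 months of exposure are over. The second is completeness: if a child has only a baseline and a 12-month value, missing the final visit leaves nothing after baseline for liver tests, and possibly nothing for FEV1. The tests planned for these outcomes have no way to use such a child.

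**Working it through.** No figure in the plan depends on this point, so the check sets the passages side by side and then counts.

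**Schedule by item (months)**

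| Item | Table 1 | Methods 3 and 4 |
|---|---|---|
| Routine panel | blood at 0, 6, 12, content not stated | 0 and 12 |
| Four stored samples | same row | no visit stated; frozen |
| FEV1 | pulmonary function at 0, 12 | every clinic attendance |
| Full spirometry | pulmonary function at 0, 12 | 0 and 12 |

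**Blood, two readings**

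1. The 6-month draw is for the stored samples only (1 + 0.5 + 0.5 + 0.5 = 2.5 ml). Both places are then consistent. The routine panel has 2 readings, with 0 between baseline and the end of treatment. Cytokines and lipid mediators do not fill the gap, because they are analysed later.
2. The Table 1 row includes the routine panel. There are then 3 readings, and the timing in Methods section 4 is wrong.

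The text does not decide between these. Under the first there is no on-treatment result before the end; under the second there is an error to correct.

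**FEV1, two readings**

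1. The Table 1 row means full spirometry, which it matches exactly. Routine FEV1 then has no row. Whether a 6-month value is recorded depends on whether a clinical visit includes the 6-month study visit. That term is not defined, and the anthropometry section speaks of scheduled visits instead.
2. The row covers all lung function. FEV1 then has 2 time points in Table 1 and 3 in Methods section 3 (if the 6-month visit counts), and the two conflict.

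**Size of the completeness problem**

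Inputs (Sample size section): 90 enrolled, withdrawal close to 10%, 84 needed.

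- Expected withdrawals: 0.10 × 90 = 9.
- Loss that the enrolment figure actually covers: 90 − 84 = 6, or 6/90 = 6.7%.
- Assumption: a child who withdraws does not attend at 12 months. Up to about 9 children then have no routine biochemistry after baseline, and none has a Table 1 lung function value after baseline.
- A 6-month value helps only those who leave after month 6. The documents do not give that number; it lies between 0 and 9. If withdrawals were spread evenly over the year (an assumption), it would be 9 × 6/12 = 4.5, so 4 or 5 children.

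**The case against.** The strongest reply is that nothing strictly contradicts. A generic blood row in an outline table is satisfied by drawing the stored samples at 6 months, and IGF-I and the fatty acid profile, as secondary outcomes, give that draw a purpose. The pulmonary row agrees with the full-spirometry item, and routine FEV1 is listed separately. This stands: a flat contradiction is not shown. But no passage says what the 6-month blood is for, and on this same benign reading no routine result is scheduled during treatment and FEV1 has no row.

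A reader might also infer that the protocol names liver and inflammatory risks of the supplement and then leaves them unmonitored. The documents do not support that.

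- On the liver, the background reports an association in CF, "suggesting that the concentrations of polyunsaturated fatty acids (PUFA) might contribute to the unexplained liver affection in many of the patients". It does not describe a harm of supplementation, and it elsewhere cites improved liver parameters after long-term supplementation.
- On inflammation, it reports why other centres hesitate over linoleic acid, namely that "it's a substrate for AA and thereby also for the pro-inflammatory lipid mediators". It then argues against the worry, citing lower arachidonic acid with supplementation and no reported rise in inflammatory markers in healthy people.
- The RISK-BENEFIT section expects no adverse effects.

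That expectation may be optimistic and does not replace measurement, but these are reported concerns, not named risks.

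Nor would a site necessarily learn nothing at 6 months. Usual care continues, exacerbations and antibiotics are registered, and coordinators are in monthly contact. None of these, however, schedules a liver test or blood count. It is also unsupported to say that children who stop early are mainly those who did not tolerate the supplement; the documents give no reasons for withdrawal.

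**Conclusion.** The point holds as an unclear 6-month schedule with a modest consequence. On the Methods text, 0 routine liver, blood-count or CRP results fall between baseline and the end of treatment for all 90 children. Whether a 6-month FEV1 is collected as study data is undefined. If the Table 1 blood row was meant to include the routine panel, the gap in blood results disappears and what remains is a text error.

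The gain in analysis is small: some number below the roughly 9 expected withdrawals, and none for children who leave before month 6. It rests on the assumption that withdrawn children miss the final visit. The gain in information during treatment applies to every child seen at 6 months. Because the visit and the draw already exist, the change is worth making, but this is not evidence of a missed safety signal.

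**What to change.** 1. Reconcile Table 1 with Methods sections 3 and 4. State the visits for the routine panel and for each of the four stored samples, and say what the 6-month blood is for.
2. Run the core routine panel (liver enzymes, bilirubin, blood count, CRP) on the 6-month blood, and state whether that visit is fasting, since the panel is specified as fasting.
3. Give FEV1 its own row in Table 1 at 0, 6 and 12 months, separate from full spirometry, and record the 6-month value in the study file.
4. Analyse FEV1 and the liver tests with a between-arm repeated-measures model like the one for the primary outcome (treatment, categorical time and their interaction, random intercept). The paired tests in section 9 do not use a third time point. With the model, a child who leaves after month 6 still contributes.

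**Cost:** one routine panel per child (up to 90), somewhat more blood than the 2.5 ml of stored samples, possibly fasting at 6 months, extra columns in the data file and a little more analysis. No extra visit or venepuncture is needed. No rule for clinical action on the results is proposed here.

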Patients with CF, carrying 2 severe mutations referred to Class I and II, i.e. mutations associated with more severe LA deficiency and more severe clinical symptoms, (like delF508, 394delTT) are included after informed consent. The reason for including only those with clinically more severe phenotype is that those have pancreatic insufficiency and also other symptoms more expressively related to genotype (see above). Exclusion criteria will be pregnancy and transplantation and age above 15 and below 5 years (due to pulmonary function tests) and severe liver disease (cirrhosis, portal hypertension). The patients shall not have taken any lipid supplements for 2 months before inclusion and not be treated with any modulators (like Orkambi, Trikafta).

The patients will keep to their ordinary treatment of PERT and vitamins and that for the pulmonary symptoms and infections. No special dietary recommendations will be given, but PERT might be increased, when the supplement is given and that shall be registered. Number of pulmonary exacerbations and type of treatment, including antibiotics, are registered and also compared with the year before the study.

Sample size

A sample of 84 patients (42 per group) will ensure that a two-sided test with α =0.05 has 80% power to detect a 0.5 mean difference in 1-year change in weight-

for-age Z-score, assuming a pooled standard deviation of 0.8. This last figure has been obtained from a previous intervention study on cystic fibrosis patients (Alicandro et al. 2013). Since we expect a withdrawal rate of close to 10%, we planned to enroll 90 patients (45 per groups). The patients and caregivers will be informed by oral and written information and included after informed consent. The study is approved by local Ethic Committees and by the one at Karolinska Institutet and the study is performed according to the Helsinki Declaration.

Design

The study is designed as a double-blind randomized clinical trial

The patients will be randomized to either

- treatment A: linoleic acid (12 g for children 5-15 years) + 600 mg algeal DHA
- treatment B: oleic acid (12 g for children 5-15 years) + 600 mg algeal DHA

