Sampling. Mixture in local laboratory with freezing of an aliquote for later transport to Poznan

6. *Metabolic tests*

- Urine sample for 8-isoprostanate and lipid mediators as eicosanoids, docosanoids and linoleic acid metabolites (directly to freezer -80 each sample in 2 x 8 ml and in 4 x 2 ml) for later analyses in Stockholm.
- Indirect calorimetry at start and after 12 months (if available in the hospital).
- Sweat test at start and after 12 months. **Both sodium** and chloride analyses.
- Oral glucose tolerance test.

7. *Quality of life.*

Quality of life will be assessed through the CF Questionnaire Revised (CFQ), a disease-specific tool that measures health-related quality of life in patients with

CF. There are different versions of the questionnaire: two for children over 6 years, one to be completed by the child and one to be completed by parent (CFQ Child and CFQ-Parent, respectively).

8. Compliance with the treatment

Compliance with the treatment will be evaluated by monthly contact with the study coordinator of respective centre, when not used vials will be registered and new supplied. The patients are asked to make a dairy over the daily intake also reported monthly to the coordinator. Extent of physical activity shall be notified.

9. Statistics

All data will be collected in identical Excel files and analysed in one center at end study.

The main analysis will be carried out on the intention-to-treat population defined as all randomized patients. We will also conduct a secondary analysis on the per-protocol population excluding patients not receiving the allocated treatment for more than 2 months.

Between-treatment differences in the primary outcome across time points will be evaluated by fitting random intercept linear mixed-effects models. Mixed effects model can account for intra-correlated repeated measures on the same subjects and accommodate missing data due to dropouts. The models will include the z-score of BMI as response variable, treatment, time and time x treatment interaction as independent variables. The model coefficients for the time x treatment interaction will be considered an estimate of the treatment effect on changes in the study outcome. Time will be included in the model as categorical variable with the following categories: baseline (pre-treatment), +6 months and +12 months from treatment allocation.

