## 9. Statistics

All data will be collected in identical Excel files and analysed in one center at end study.

The main analysis will be carried out on the intention-to-treat population defined as all randomized patients. We will also conduct a secondary analysis on the per-protocol population excluding patients not receiving the allocated treatment for more than 2 months.

Between-treatment differences in the primary outcome across time points will be evaluated by fitting random intercept linear mixed-effects models. Mixed effects model can account for intra-correlated repeated measures on the same subjects and accommodate missing data due to dropouts. The models will include the z-score of BMI as response variable, treatment, time and time x treatment interaction as independent variables. The model coefficients for the time x treatment interaction will be considered an estimate of the treatment effect on changes in the study outcome. Time will be included in the model as categorical variable with the following categories: baseline (pre-treatment), +6 months and +12 months from treatment allocation.

Secondary and explanatory outcomes will be compared across treatment groups using the paired t-test for normally distributed variables, otherwise the non-parametric Wilcoxon signed-rank test for dependent samples will be used.

A stratified analysis by sex will be performed.

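### The primary random-intercept model ties the 12-month standard error to an unstated assumption about half-year changes, and the primary test is not named

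*Protocol*

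**What the plan says.** Section 9 (Statistics) has the same wording in the protocol and the SAP. "Between-treatment differences in the primary outcome across time points" are to be "evaluated by fitting random intercept linear mixed-effects models", with BMI z-score as the response. On the time scale: "Time will be included in the model as categorical variable with the following categories: baseline (pre-treatment), +6 months and +12 months". On the effect: "The model coefficients for the time x treatment interaction will be considered an estimate of the treatment effect on changes in the study outcome".

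The only remark on within-patient correlation is general: "Mixed effects model can account for intra-correlated repeated measures on the same subjects and accommodate missing data due to dropouts". Neither document states a residual covariance structure, a random slope, a robust standard error or a sensitivity analysis for the covariance.

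The Sample size section of the protocol is built on one time point. It claims "80% power to detect a 0.5 mean difference in 1-year change" in weight-for-age Z-score, "assuming a pooled standard deviation of 0.8".

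**The concern.** A random intercept with independent, equal-variance residuals forces the same correlation on every pair of visits (compound symmetry). In growth data, measurements 12 months apart may well be less alike than measurements 6 months apart. If so, the 12-month change varies more than the model allows, and the 12-month interval is too narrow. If the pattern runs the other way, the interval is too wide and power is lost.

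The 12-month coefficient is where this matters, because the trial is sized on 1-year change and treatment lasts 12 months. Yet section 9 speaks of differences across visits and of coefficients in the plural, so a 12-month contrast and a joint test of both interaction terms are both open. The two behave differently when the covariance is wrong.

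**Working it through.** **Inputs.** From the protocol: 42 per arm, difference 0.5, SD 0.8 for 1-year change in weight-for-age Z-score, two-sided 5%, 90 enrolled with about 10% withdrawal, visits at 0, 6 and 12 months. The documents give no SD for 6-month change, no between-visit correlation and no SD for BMI z-score. Every variance pattern below is therefore an assumption.

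**The plan's own figure.** The normal formula gives 2 × (1.96 + 0.842)² × 0.8² / 0.5² = 40.2, so 41 per arm. The t-test gives power of 79.8% at 41 per arm and 80.8% at 42. The stated 42 per arm reproduces.

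**The condition.** Write V0-6, V6-12 and V0-12 for the variances of the three changes. With complete data, the 12-month interaction estimate is the difference in mean 0-12 month change, and its true variance depends on V0-12. The random-intercept model uses (V0-6 + V6-12 + V0-12)/3 instead. Hence

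- SE ratio (model / true) = √[(V0-6 + V6-12 + V0-12) / (3 × V0-12)]
- type I error = 2 × (1 − Φ(1.96 × ratio))

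The ratio is below 1 exactly when V0-12 exceeds (V0-6 + V6-12)/2.

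**Results.** Let k be the SD of 6-month change divided by the SD of 12-month change. With equal half-year variances, ratio = √[(1 + 2k²)/3]. For example, at k = 0.9 it is √(2.62/3) = 0.934.

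| Assumed pattern | SE ratio | Type I error, 12-month test |
|---|---|---|
| k = 1 | 1.000 | 5.0% |
| k = 0.95 | 0.967 | 5.8% |
| k = 0.9 | 0.934 | 6.7% |
| k = 0.75 | 0.842 | 9.9% |
| k = 0.707 (random walk, no visit-to-visit noise) | 0.816 | 11.0% |
| Random drift is a quarter of V0-12, rest visit noise | 0.957 | 6.1% |
| Random drift is half of V0-12, rest visit noise | 0.913 | 7.4% |
| V0-6 / V6-12 / V0-12 = 0.8 / 1.2 / 1.0 | 1.000 | 5.0% |
| 0.7 / 1.4 / 1.0 | 1.017 | 4.6% |
| 1.2 / 1.2 / 1.0 | 1.065 | 3.7% |

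**Check by simulation, complete data** (no treatment effect, 45 per arm, 100,000 runs per row).

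| Pattern | Random intercept, 12-month | Random intercept, joint 2-df | 12-month test on its own change variance |
|---|---|---|---|
| k = 1 | 5.0% | 5.0% | 5.0% |
| k = 0.9 | 6.6% | 4.9% | 4.9% |
| k = 0.75 | 9.7% | 5.6% | 4.9% |
| Random walk | 11.0% | 6.0% | 5.1% |
| 0.8 / 1.2 / 1.0 | 5.0% | 5.3% | 5.0% |
| 0.7 / 1.4 / 1.0 | 4.7% | 5.5% | 5.0% |

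**With withdrawal** (90 enrolled, 9 missing at random at 12 months only, assumed baseline variance 1 and V0-12 = 0.64, REML, 8,000 runs, simulation error about 0.3 point). The unstructured test used a t distribution with 79 df in place of Kenward-Roger.

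| Pattern | Planned random intercept | Random intercept, corrected robust SE | Unstructured |
|---|---|---|---|
| k = 1 | 5.3% | 5.2% | 4.9% |
| k = 0.9 | 6.4% | 4.8% | 4.6% |
| k = 0.75 | 10.4% | 5.0% | 4.9% |
| Random walk | 11.7% | 5.5% | 5.3% |
| 0.8 / 1.2 / 1.0 | 5.4% | 5.1% | 4.6% |

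Robust standard errors without a small-sample correction gave 5.4 to 6.1%.

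**The case against.** A random-intercept model with categorical time is a recognised, pre-specified analysis of three visits, and nothing in the documents shows that its assumption fails. The 10 to 11% figures need k of about 0.75 or less. The top one is a random walk without measurement noise, which is extreme for repeated weight and height. The mixed patterns give 6 to 7%, and some patterns are nominal or conservative. Section 9 can also be read as a joint interaction test, for which the problem nearly vanishes. The case for the 12-month contrast comes from a sample-size text about weight-for-age Z-score, while the model is for BMI z-score. The algebra is exact only for complete data.

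Most of this stands, and it limits how strongly the point can be put: inflation is possible but not shown, and the direction is unknown. The complete-data qualifier matters little, since the results with 10% withdrawal follow the same pattern. What the objection does not remove is that the validity of a 12-month p-value rests on an unstated and unsupported assumption that is easily avoided. That the text admits two primary tests can be seen without any variance assumption.

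**Conclusion.** The point holds as a recommended improvement. The 12-month standard error is right only if the variance of the 12-month change equals the average of the two half-year variances, and the plan neither supports this nor guards against its failure. Depending on the assumed pattern, the 12-month standard error is from 18% too small to about 6% too large, and type I error runs from 11% down to 3.7%. Moderate departures in the unfavourable direction give about 6 to 7%. A joint test would be only slightly affected. With complete data the point estimate is not in question; only its standard error, interval and p-value are. The SE ratios and error rates depend only on the relative variances, so using the weight-for-age SD does not affect them.

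**What to change.** In section 9 of both documents, keep the fixed effects and replace the random intercept with an unstructured within-patient covariance over the three visits, fitted by REML with Kenward-Roger degrees of freedom. Name the treatment difference in 0-12 month change as the primary test. State a fallback for non-convergence: the planned random-intercept model with patient-level robust standard errors and a small-sample correction.

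The cost is two sentences per document and four more covariance parameters (6 instead of 2), which about 90 patients with three visits can support. Where the 12-month change is the more variable, the interval becomes wider than under the planned model, by the inverse of the SE ratio: 1/0.934 = 1.07 at k = 0.9 (7%), 19% at k = 0.75 and 22% for a random walk. That is its correct width.

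The planned sample size does not change. At the stated SD of 0.8, which is not for BMI z-score, a t-test on 1-year change has 80.8% power at 42 per arm and 79.3% with the 81 completers left after 10% withdrawal from 90 (90 × 0.9 = 81). If those who withdraw still have a 6-month visit, the unstructured model uses it. Simulated power is then about 80 to 81%, assuming half the effect at 6 months (4,000 runs, error about 0.6 point).

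### The primary model gives each randomised arm its own baseline mean; a shared baseline mean would usually estimate the 12-month effect more precisely, by an amount the documents cannot fix

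*Protocol*

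**What the plan says.** Section 9 (Statistics) is worded identically in the Protocol and the SAP. The primary outcome is analysed by "fitting random intercept linear mixed-effects models", with BMI Z-score as response and "treatment, time and time x treatment interaction as independent variables". Time is categorical, with levels "baseline (pre-treatment), +6 months and +12 months from treatment allocation". On the estimate, the text says: "The model coefficients for the time x treatment interaction will be considered an estimate of the treatment effect on changes in the study outcome". On the population: "The main analysis will be carried out on the intention-to-treat population defined as all randomized patients".

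Neither document sets the two baseline means equal or enters baseline as a covariate. The Protocol's Design section allocates patients at random, half to each treatment.

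The Sample size section of the Protocol is written for weight-for-age Z-score. It gives a "two-sided test with α =0.05 has 80% power to detect a 0.5 mean difference in 1-year change in weight"-for-age Z-score, "assuming a pooled standard deviation of 0.8", with 42 evaluable patients per group. It does not say whether 0.8 is the SD of the one-year change or of a single score.

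**The concern.** Because baseline is a level of the response and treatment has a main effect, that main effect is the between-arm difference at baseline. Baseline is measured before treatment in randomised arms, so its true value is zero. Estimating it anyway passes chance baseline imbalance in full into the 12-month contrast. A model with one common baseline mean removes only the part of the imbalance that the baseline/12-month relation predicts, and that usually gives a smaller variance.

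What is at stake is precision. If 0.8 is the SD of change, the trial has almost no slack: two-sample t-test power is 80.8% at 42 per arm and 79.8% at 41. The baseline is already scheduled for every patient, so any gain needs no new data.

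The random intercept raises a second, separate question. It imposes one common correlation on all three pairs of visits. If that is wrong, the model's standard error for the 12-month contrast is wrong too, whether or not the baseline mean is shared.

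**Working it through.** **Inputs.** From the Protocol's Sample size section: difference 0.5, SD 0.8, two-sided 5%, 80% power, 42 per arm. From section 9: three visits, random intercept, free treatment main effect. Assumed, because the documents give neither: rho and the ratio of the 12-month SD (s12) to the baseline SD (s0).

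**1. The plan's own figure.** The normal approximation is 2 × (1.960 + 0.842)² × 0.8² / 0.5² = 40.2, so 41 per arm. The t-test needs 42 (power 0.798 at 41, 0.808 at 42). The stated 84 is reproduced.

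**2. What the planned coefficient is.** In 300 simulated complete-data trials per scenario, the fitted 12-month interaction equalled the simple difference in mean change, with a largest gap of about 3e-15.

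**3. Variance ratio, shared against separate baseline means.**
- General: s12²(1 − rho²) / (s0² + s12² − 2·rho·s0·s12).
- Equal SDs: (1 − rho²) / [2(1 − rho)] = (1 + rho)/2.
- The ratio is 1, so there is no gain, when rho·s12/s0 = 1, that is, when the slope of the 12-month value on baseline is 1.

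With 45 per arm and 4 lost (2 after baseline, 2 after 6 months), under equal variances and correlations, the ratio is 0.77 at rho 0.5, 0.91 at 0.8 and 0.95 at 0.9. The gain survives dropout.

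**4. Power if 0.8 is the SD of change** (carried over to BMI Z-score; equal SDs and visit correlations; 42 per arm). Planned model: SE = 0.8 × √(2/42) = 0.1746. The random-intercept model pools residual variance over three visits (about 164 df), so its power is 81.3%, against 80.8% for the t-test with 82 df. Shared baseline with unstructured covariance: SE = 0.1746 × √[(1+rho)/2], inflated by √(1 + 1/80) for the estimated slope, with 81 df.

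| rho | (1+rho)/2 | SE before inflation | Power |
|---|---|---|---|
| 0.50 | 0.75 | 0.151 | 90.1% |
| 0.68 | 0.84 | 0.160 | 86.6% |
| 0.80 | 0.90 | 0.166 | 84% |
| 0.90 | 0.95 | 0.170 | 82.3% |
| 0.95 | 0.975 | 0.172 | 81.3% |

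With a slope of exactly 1 the result is 80.3%, about 1 point below the planned 81.3%.

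Unequal SDs at rho 0.8 (t-test calculation, slope treated as known, against 80.8%): 89.0% if the 12-month SD is 10% smaller, 82.0% if 10% larger, 80.8% if 25% larger.

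**5. Power if 0.8 is the SD of the score.** The SD of change is 0.8√[2(1 − rho)] and the shared-baseline SD is 0.8√(1 − rho²). T-test power, slope treated as known:

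| rho | Separate baselines | Shared baseline |
|---|---|---|
| 0.3 | 66.7% | 84.3% |
| 0.5 | 80.8% | 90.5% |
| 0.7 | 95.5% | 97.7% |
| 0.8 | 99.4% | 99.7% |

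**6. Covariance, a separate check.** With complete data and equal variances, the random intercept in effect uses the average of the three visit correlations. Its SE for the 12-month contrast relative to the true SE is therefore about √[(1 − average)/(1 − rho)]. For adjacent-visit correlations of 0.85 and rho 0.75, the average is (0.85 + 0.85 + 0.75)/3 = 0.817, and √(0.183/0.25) = 0.86. Size of the two-sided 5% test in 40,000 simulations, complete data:

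| Adjacent, rho (assumed) | Planned | Shared baseline, random intercept | Shared baseline, unstructured |
|---|---|---|---|
| 0.80, 0.80 | 0.050 | 0.051 | 0.051 |
| 0.85, 0.75 | 0.096 | 0.091 | 0.051 |
| 0.85, 0.7225 | 0.101 | 0.097 | 0.049 |
| 0.90, 0.80 | 0.109 | 0.106 | 0.049 |
| 0.90, 0.81 | 0.103 | 0.100 | 0.048 |

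In the four unequal cases the planned model's SE is 0.82 to 0.86 of the true SE. Sharing the baseline mean alone barely changes the size.

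**The case against.** The strongest reply is that nothing here is an error. A mixed model with treatment, categorical time and their interaction is conventional, its contrast is unbiased under randomisation, and it matches the difference in one-year change used for the sample size. This stands, and a reader who inferred that the planned analysis is biased, or that it does not answer the trial's question, would go further than the documents allow. It does not make the point idle: the alternative uses data already collected and its downside is small.

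A second reply is that the gain may be negligible. Holding the SD of change at 0.8 forces the score SD to 0.8/√[2(1 − rho)]: 0.80 at rho 0.5, 1.00 at 0.68, 1.26 at 0.8 and 1.79 at 0.9. If the score SD were 1.0 (assumed), power without adjustment would already be 94.7% at rho 0.8 and 99.9% at 0.9. This also stands. A reader might infer that the trial is short of power, or that some 10 points are there for the taking. The documents support neither, because they give no rho and do not say what the 0.8 measures.

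A third reply is that the covariance problem is one of validity and should not lend weight to an efficiency argument. That is right, and the two are kept apart here. Nor do the documents show that the type I error is inflated: the 9-11% rests on assumed correlations that weaken with time, and under equal correlations the size is 5%.

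**Conclusion.** The point holds as a matter of efficiency. The planned contrast is valid but usually less precise than one with a shared baseline mean. The variance ratio of (1+rho)/2 requires equal variances at baseline and 12 months; it does not depend on the 0.5 or the 0.8. The power figures rest further on what the 0.8 means and on carrying it from weight to BMI Z-score. Over the cases examined, the change in power runs from a loss of about 1 point (slope on baseline exactly 1) to a gain of 10 points or more at low rho. Its true size is unknown.

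The covariance point is separate and conditional: if adjacent visits correlate more strongly than baseline and 12 months, the planned test is anti-conservative, and sharing the baseline mean does not cure it.

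Both are met by one optional but worthwhile change of wording. It is not a correction of bias.

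**What to change.** Amend section 9 in both the Protocol and the SAP before unblinding:

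- Keep baseline BMI Z-score as a response for all randomised patients.
- Omit the treatment main effect, and include time plus time-by-treatment terms at 6 and 12 months only, so that both arms share one baseline mean.
- Name the 12-month contrast, linoleic acid minus oleic acid, as the primary estimate.
- Replace the random intercept with an unstructured covariance over the three visits, and state a small-sample degrees-of-freedom method such as Kenward-Roger.

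The cost is wording, four more covariance parameters (six instead of two) and one fewer mean parameter. The loss of power is about 1 point at worst. No patients, visits or measurements are added, and the analysis population stays as planned. Stating whether the 0.8 is the SD of change or of the score, and the rho expected, would let the sponsor put a figure on the gain.
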